2. STUDY OBJECTIVES AND ENDPOINTS

2.1. Objectives

This study includes six cohorts: 1) a monotherapy cohort to evaluate the tolerability and safety of PF-04449913 administered orally as a single agent to Japanese patients with select advanced hematologic malignancies, 2) two combination cohorts of Japanese patients with previously untreated AML or high-risk MDS assessing the tolerability and safety of the following two combination regimens: (i) LDAC plus PF-04449913 in the unfit patient population for patients who are unable to receive intensive chemotherapy (Combination Cohort 1, unfit patients), and (ii) cytarabine/daunorubicin (7:3) plus PF-04449913 in the fit patient population for patients who are able to receive intensive chemotherapy (Combination Cohort 2, fit patients), 3) expansion cohort of LDAC combination for efficacy in which

PF-04449913 is administered with LDAC in 15 Japanese patients with previously untreated AML or high-risk MDS, 4) one combination cohort to evaluate the tolerability and safety of PF-04449913 administered in combination with azacitidine to 6 Japanese patients with previously untreated AML who are eligible for non-intensive chemotherapy, and 5) a continuation cohort (monotherapy cohort) in which PF-04449913 is administered as a single agent in 1 Japanese MF patient who has been treated in Study B1371013. The study objectives for each cohort are outlined below. A total of up to 49 patients will be treated across all six cohorts.

Monotherapy Cohort:

Primary Objective

- To determine the safety and tolerability of PF-04449913 administered as monotherapy in Japanese patients with select advanced hematologic malignancies.

Secondary Objectives

- To evaluate the pharmacokinetics (PK) of PF-04449913 as monotherapy in Japanese patients with select advanced hematologic malignancies;
- To evaluate the pharmacodynamics (PD) of PF-04449913 as monotherapy in Japanese patients with select advanced hematologic malignancies;
- To assess preliminary evidence of clinical efficacy of PF-04449913 administered as monotherapy in Japanese patients with select advanced hematologic malignancies.

Combination Cohorts 1 and 2 (Unfit and Fit Patients):

Primary Objective

- To determine the safety and tolerability of PF-04449913 administered in combination with Low-dose Ara-C (LDAC) (Combination Cohort 1, unfit patients), or cytarabine/daunorubicin (7:3) (Combination Cohort 2, fit patients) to Japanese patients with previously untreated AML, or high-risk MDS.

Secondary Objectives

- To evaluate the PK of PF-04449913 and potential drug-drug interaction (DDI) between PF-04449913 and LDAC (Combination Cohort 1, unfit patients) or cytarabine/daunorubicin (7:3) (Combination Cohort 2, fit patients) administered to Japanese patients with previously untreated AML or high-risk MDS;
- To evaluate the PD of PF-04449913 administered in combination with LDAC (Combination Cohort 1, unfit patients) or cytarabine/daunorubicin (7:3) (Combination Cohort 2, fit patients) to Japanese patients with previously untreated AML or high-risk MDS;

- To assess preliminary evidence of clinical efficacy (including disease-specific measures) of PF-04449913 administered in combination with LDAC (Combination Cohort 1, unfit patients) or cytarabine/daunorubicin (7:3) (Combination Cohort 2, fit patients) to Japanese patients with previously untreated AML or high-risk MDS.

Expansion Cohort of LDAC combination for efficacy (Unfit Patients):

Primary Objective

- To evaluate the efficacy (DMR rate) of PF-04449913 administered in combination with LDAC to Japanese patients with previously untreated AML or high-risk MDS.

Secondary Objectives

- To evaluate the safety of PF-04449913 administered in combination with LDAC to Japanese patients with previously untreated AML or high-risk MDS;
- To evaluate the efficacy (including OS) of PF-04449913 administered in combination with LDAC to Japanese patients with previously untreated AML or high-risk MDS;
- To evaluate the PK and PD of PF-04449913 administered in combination with LDAC to Japanese patients with previously untreated AML or high-risk MDS.

Combination Cohort 3 (Azacitidine Combination):

Primary Objective

- To determine the safety and tolerability of PF-04449913 administered in combination with azacitidine in Japanese patients with previously untreated AML who are eligible for non-intensive chemotherapy.

Secondary Objectives

- To evaluate the PK of PF-04449913 and azacitidine when administered to Japanese patients with previously untreated AML who are eligible for non-intensive chemotherapy;
- To evaluate the PD of PF-04449913 administered in combination with azacitidine to Japanese patients with previously untreated AML who are eligible for non-intensive chemotherapy;
- To assess any preliminary evidence of clinical efficacy including OS of PF-04449913 administered in combination with azacitidine to Japanese patients with previously untreated AML who are eligible for non-intensive chemotherapy.

Continuation Cohort (Monotherapy Cohort):

- To assess the safety of PF-04449913 administered as monotherapy in the Japanese MF patient who has been treated with PF-04449913 in Study B1371013 and without documented objective progression of disease and with continuous clinical benefit at the time the patient discontinued from Study B1371013.

2.2. Endpoints

Monotherapy Cohort:

Primary Endpoint

- First-cycle dose-limiting toxicities (DLTs); Type, incidence, severity [graded by the National Cancer Institute (NCI) Common Terminology Criteria for Adverse Events (CTCAE), Version 4.0], timing, seriousness, and relatedness of adverse events; vital signs and laboratory test abnormalities.

Secondary Endpoints

- PK parameters of PF-04449913;
- Potential biomarkers of target modulation, response or resistance to PF-04449913 in Japanese patients with advanced hematologic malignancies;
- Objective disease response as assessed using the response criteria for the hemotologic disease under study.

Combination Cohorts 1 and 2 (Unfit and Fit Patients):

Primary Endpoint

- First-cycle DLTs; Type, incidence, severity (graded by NCI-CTCAE, Version 4.0), timing, seriousness, and relatedness of adverse events; vital signs and laboratory test abnormalities.

Secondary Endpoints

- PK parameters of PF-04449913 with: (i) LDAC, and (ii) cytarabine/daunorubicin (7:3) combinations;
- Potential biomarkers of target modulation, response or resistance to PF-04449913 in combination with chemotherapy in Japanese patients with previously untreated AML or high-risk MDS;
- Objective disease response, as assessed using the appropriate response criteria for AML or MDS.

- Survival status (only Combination Cohort 1)

Expansion Cohort of LDAC combination for efficacy (Unfit Patients):

Primary Endpoint

- DMR rate

Secondary Endpoints

- Type, incidence, severity (graded by NCI CTCAE, Version 4.0), timing, seriousness, and relatedness of adverse events; vital signs and laboratory test abnormalities;
- OS;
- Objective disease response, as assessed using the appropriate response criteria for AML or MDS; complete remission (CR) rate; duration of response; time to response;
- PK and potential biomarkers of target modulation, response or resistance to PF-04449913 in combination with LDAC in Japanese patients with previously untreated AML or high-risk MDS.

Combination Cohort 3 (Azacitidine Combination):

Primary Endpoint

- First-cycle DLTs; Type, incidence, severity (graded by NCI CTCAE, Version 4.0), timing, seriousness, and relatedness of adverse events; vital signs and laboratory test abnormalities.

Secondary Endpoints

- PK parameters of PF-04449913 and azacitidine;
- OS;
- Potential biomarkers of target modulation, response or resistance to PF-04449913 in combination with azacitidine in Japanese patients with previously untreated AML who are eligible for non-intensive chemotherapy;
- Objective disease response, as assessed using the appropriate response criteria for AML; duration of response; time to response

Continuation Cohort (Monotherapy Cohort):

- Type, severity (graded by NCI CTCAE, Version 4.0), timing, seriousness, and relatedness of adverse events; laboratory test abnormalities.

Efficacy-related data will not be collected in this cohort.

3. STUDY DESIGN

3.1. Study Overview

This is an open-label, multi-center, Phase 1 study of PF-04449913 in Japanese patients. PF-04449913 will be administered orally as a single agent in up to 15 patients with select advanced hematologic malignancies (Monotherapy Cohort), or in combination with LDAC (Combination Cohort 1, unfit patients) or cytarabine and daunorubicin (7:3) (Combination Cohort 2, fit patients) in up to 12 previously untreated patients with AML or high-risk MDS. PF-04449913 will be administered in combination with LDAC in a total of 15 patients with previously untreated AML or high-risk MDS (Expansion Cohort of LDAC combination for efficacy, unfit patients). PF-04449913 will be also administered in combination with azacitidine in a total of 6 patients with previously untreated AML who are eligible for non-intensive chemotherapy (Combination Cohort 3, Azacitidine Combination). PF-04449913 will be administered as a single agent in 1 Japanese MF patient who has been treated in Study B1371013 and on the study treatment at the time of the study discontinuation [Continuation Cohort (Monotherapy Cohort)].

3.1.1. Monotherapy Cohort

The monotherapy cohort will evaluate the safety and tolerability of PF-04449913 administered as a single agent once daily continuously. Cycle 1 will be preceded by a single lead-in dose of PF-04449913 administered on Day -5 (lead-in period) in order to characterize the single-dose PK of PF-04449913 prior to initiation of continuous dosing in the first cycle of treatment. From Cycle 1/Day 1 onwards, PF-04449913 will be administered continuously once daily, in 28-day cycles.

A standard 3+3 dose escalation design will be used to evaluate the tolerability of PF-04449913 with 3-6 patients per dose level. Two dose levels of PF-04449913 (Dose Level 1: 50 mg QD and Dose Level 2: 100 mg QD) will, in the first instance, be investigated in sequential cohorts of patients. Intermediate (such as 80 mg QD) or lower dose levels (such as 25 mg) may be explored at any time during the study if this is clinically and scientifically warranted. Study centers will receive a notification if additional dose levels are explored.

The DLT evaluation period includes the PK lead-in period, and the first cycle of treatment. Dose escalation to the 100 mg QD dose level will occur if $<1/3$ or $<2/6$ patients at the 50 mg QD dose level experience dose-limiting toxicities (DLT) during the first cycle of treatment. If ≤ 1 patient experiences a DLT event in the first 3 patients, an additional 3 patients will be enrolled to give a total of 6 patients in the 100 mg QD cohort. If ≤ 1 of the 6 patients experiences a DLT by the end of Cycle 1, the tolerability of the 100 mg QD dose level in the monotherapy cohort will be deemed confirmed, and the study will proceed to the combination cohort. If 2 or more of the 6 patients treated at 100 mg QD in the monotherapy cohort experience a DLT by the end of Cycle 1, an intermediate dose level (80 mg QD) may be explored in the monotherapy cohort prior to proceeding with the combination cohort. If two or more of the 3 or 6 patients treated at 50 mg QD in the monotherapy cohort

experiences a DLT by the end of Cycle 1, the dose escalation will be terminated, and a lower dose may be explored.

As of 7 August 2014, it was decided by the study team that a lower dose level (25 mg QD) will be explored in the study, since evaluation of PD data at the 25 mg QD dose is scientifically warranted. Up to 3 patients will be enrolled at the 25 mg dose level. DLT evaluation will be performed on this dose level, however, it will not be used for the dose escalation decision, or for the determination of whether or not to proceed with the combination cohort. The Sponsor will discuss with the Investigator to confirm that there is no safety issue for patients enrolled at this dose level.

Treatment with PF-04449913 may continue for up to 12 cycles or until disease progression or relapse, patient withdrawal, or unacceptable toxicity occurs (whichever is first). Patients who complete 12 cycles of treatment will be deemed to have completed the study. However, patients who complete 12 cycles of study treatment who demonstrate clinical benefit with manageable toxicity, and are willing to continue receiving the study treatment, may be given the opportunity to do so following agreement between the Investigator and Sponsor, and pending study drug availability. If treatment continues beyond 12 cycles, study procedures should continue to be performed as per [Table 1](#) (See Schedule of Activities).

The study may at any time evaluate additional dose levels of single-agent PF-04449913 based upon the emerging data from the ongoing pre-clinical and clinical studies, following discussion between the Investigators and the Sponsor.

3.1.2. Combination Cohorts

The combination cohorts will evaluate the safety and tolerability of PF-04449913 at the starting dose of 100 mg once daily continuously administered in combination with 3 different chemotherapy regimens.

Combination Cohort 1 (Unfit Patients):

In this cohort, patients who are “unfit for intensive chemotherapy” based on predefined criteria (See Inclusion Criteria) will receive PF-04449913 once daily continuously in combination with LDAC over 28 day cycles.

A total of 6 patients will be treated in this cohort and followed up for DLT evaluation. The DLT evaluation period includes the first cycle of treatment. If ≤ 1 of the 6 patients experiences a DLT by the end of Cycle 1, the tolerability of the combination will be deemed confirmed. If 2 or more of the 6 patients experience a DLT by the end of Cycle 1, additional lower dose levels may be tested, applying identical criteria to those outlined above with respect to DLT events.

Treatment with PF-04449913 in combination with LDAC may continue for up to 12 cycles or until disease progression or relapse, patient refusal, or unacceptable toxicity occurs (whichever is first). Unfit patients who complete 12 cycles of study treatment will be deemed to have completed the study. However, patients who complete the 12 cycles of study

treatment and demonstrate clinical benefit with manageable toxicity, and are willing to continue receiving the study treatment (monotherapy of PF-04449913 or combination therapy), may be given the opportunity to do so following agreement between the Investigator and Sponsor, and pending study drug availability. If treatment continues beyond 12 cycles, study procedures should continue to be performed as listed in [Table 2](#) (Schedule of Activities). This cohort includes survival follow-up.

Expansion Cohort of LDAC combination for efficacy (Unfit Patients):

In this cohort, patients who are “unfit for intensive chemotherapy” based on predefined criteria (See Inclusion Criteria) will receive PF-04449913 once daily continuously in combination with LDAC over 28-day cycles.

A total of 15 patients will be treated in this cohort and DMR rate will be evaluated. Treatment with PF-04449913 in combination with LDAC may continue until disease progression or relapse, patient refusal, or unacceptable toxicity occurs (whichever is first). All patients will be followed for survival every 8 weeks up to 2 years from the first dose of the last patient enrolled in the study, or until death, end of the study, or patient withdrawal of consent, whichever comes first, regardless of initiation of new cancer therapy (follow-up on survival status will no longer be required after Protocol Amendment 8).

Combination Cohort 2 (Fit Patients):

In this cohort, patients defined as “fit for intensive chemotherapy” based on pre-defined criteria (See Inclusion Criteria) will receive PF-04449913 once daily continuously in combination with daunorubicin and cytarabine during induction and consolidation. For the first induction cycle only, PF-04449913 will commence on Day -3 and will then be given once daily continuously for the duration of treatment. Following completion of induction and consolidation, single-agent PF-04449913 may be given to eligible patients as maintenance therapy for a maximum of 6 cycles.

A total of 6 patients will be treated in this cohort and followed up for DLT evaluation. If ≤ 1 of the 6 patients experiences a DLT event by the end of Induction Cycle 1, the tolerability of the combination will be confirmed. If 2 or more of the 6 patients experience a DLT by the end of Induction Cycle 1, additional lower dose levels may be tested using identical criteria to those outlined above with respect to DLT events.

Treatment will continue until disease progression or relapse, patient refusal, or unacceptable toxicity (whichever is first). Fit patients who complete induction, consolidation and 6 cycles of maintenance with PF-04449913 will be deemed to have completed the study treatment. However, patients who complete the 6 cycles of maintenance and demonstrate clinical benefit with manageable toxicity, and are willing to continue receiving single-agent PF-04449913, may be given the opportunity to do so following agreement between the Investigator and Sponsor, and pending study drug availability. If treatment continues beyond 6 cycles of maintenance, study procedures should continue to be performed as listed in [Table 4](#) (Schedule of Activities).

Combination Cohort 3 (Azacitidine Combination):

In this cohort, patients with previously untreated AML and eligible for non-intensive chemotherapy will receive PF-04449913 once daily continuously at the starting dose of 100 mg in combination with azacitidine over 28 day cycles.

A total of 6 patients will be treated in this cohort and followed up for DLT evaluation. The DLT evaluation period includes the first cycle of treatment. If ≤ 1 of the 6 patients experiences a DLT by the end of Cycle 1, the tolerability of the combination will be deemed confirmed. If 2 or more of the 6 patients experience a DLT by the end of Cycle 1, the investigator and the sponsor will review all available safety data and discuss the next steps.

Since responses to azacitidine may require 4-6 cycles of administration to emerge, treatment with the study drug combination should be continued for at least 6 cycles, or until death, unacceptable toxicity, or patient refusal (whichever is first). If documentation of disease progression occurs within the first 6 cycles of study treatment, the patient **SHOULD NOT** be withdrawn from study treatment following agreement between the Investigator and Sponsor if, in the Investigator's judgment, the patient is still likely to receive clinical benefit.

[figure not shown]
Treatment with the study drug combination should be continued beyond 6 cycles of treatment until objective disease progression or relapse (unless according to the Investigator there is reasonable evidence of clinical benefit, eg, HI [hematologic improvement], to justify continuation on treatment following agreement between the Investigator and Sponsor), death, unacceptable toxicity, or patient refusal (whichever is first). All patients will be followed for survival up to 3 years from the first dose of the last patient enrolled in the study, or until death, end of the study, or patient withdrawal of consent, whichever comes first, regardless of initiation of new cancer therapy.

3.1.3. Continuation Cohort (Monotherapy Cohort)

PF-04449913 at the same dose as the patient was taking in Study B1371013 will be orally administered once daily continuously as a single agent over 28 day cycles in 1 Japanese MF patient who has been treated in Study B1371013 and without documented objective progression of disease and with continuous clinical benefit at the time the patient discontinued from Study B1371013.

In this cohort, the patient receiving PF-04449913 will continue to receive study treatment until the time of disease progression, unacceptable toxicity, death, withdrawal of consent or termination of the study by Sponsor, whichever comes first. The patient may continue PF-04449913 treatment after objective progression of disease has been determined if the patient continues to experience clinical benefit, in the opinion of the investigator, and following discussion with the Sponsor. Refer to [Appendix 7](#) for the definition of disease progression.

Figure 3 Schematic of Study Design

3.2. DLT Definition

DLTs will be classified according to CTCAE version 4.0.

In the Monotherapy Cohort, the DLT observation period will be from Day -5 to Day 28 of Cycle 1.

In Combination Cohort 1 (combination with LDAC, unfit patients) and Combination Cohort 3 (combination with azacitidine) the DLT observation period will be from Day 1 to Day 28 of Cycle 1;

In Combination Cohort 2 (combination with daunorubicin and cytarabine, fit patients) the DLT observation period will be from Day -3 to Day 21 or to Day 28 of the first induction cycle depending on when the next chemotherapy cycle is started (ie, anytime between Days 21 and 28).

Any of the following adverse events will be a DLT if considered by the Investigator to be possibly related to single-agent PF-04449913 (monotherapy cohort), to PF-04449913 in combination with chemotherapy (Combination Cohorts 1 and 2), or PF-04449913 in combination with azacitidine (Combination Cohorts 3):

1. Grade ≥ 3 non-hematologic toxicity (uncontrolled despite optimal medical management [eg, nausea, vomiting, and diarrhea]), excluding Grade ≥ 3 infection, fever (including febrile neutropenia), infusion related adverse events, electrolyte abnormalities and ALT/AST elevation that returns to Grade ≤ 1 or baseline within 7 days. Note: Allergic reactions that necessitate discontinuation of study drug will not be considered a DLT unless considered possibly related to PF-04449913.
 - In an asymptomatic patient, Grade ≥ 3 QTc prolongation (QTc ≥ 501 msec) will first require repeat testing, re-evaluation by a qualified person, and correction of reversible causes such as electrolyte abnormalities, concomitant medications that may cause QTc prolongation, or hypoxia for confirmation. If, after correction of any reversible causes, the Grade 3 prolongation persists, then the event should be considered a DLT.
2. Prolonged myelosuppression that lasts longer than 42 days from the point of detection, defined as absolute neutrophil count (ANC) $< 500/\mu\text{L}$ or platelet count $< 10 \times 10^9/\text{L}$ with a normal bone marrow ($< 5\%$ blasts and no evidence of disease or dysplasia).
3. Inability to deliver at least 80% of the planned study doses for all agents in a combination due to non-hematologic toxicities.
4. Delay of > 28 days in receiving the next scheduled cycle due to persisting non-hematologic toxicities.

Patient replacement

Patients who receive less than 80% of the planned dose of any of the study drugs in the first cycle of treatment for reasons other than treatment-related toxicities are not evaluable for DLT, and should be replaced to adequately assess the safety of study treatments. At the time of dose escalation and when proceeding to the next cohort, Sponsor will discuss with Investigator to confirm there is no safety issue of patients who are not evaluable for DLT and replaced.

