2. Between cycles: next cycle administration may be postponed due to toxicity in the previous cycle.
 - A cycle may be extended to a maximum of 56 days for non-hematologic toxicity, or to a maximum of 70 days if due to hematologic toxicity. PF-04449913 dosing should continue if observed toxicity is not deemed related to PF-04449913;
 - If a treatment interruption continues beyond Day 28 of the current cycle for any agent, then the day when full treatment (all agents in the combination) is restarted will be counted as Day 1 of the next cycle for all agents.
3. In the next cycle: dose reduction based on worst toxicity in the previous cycle.

For all drug combinations:

A study treatment related continuous treatment interruption or delay of >28 days for non-hematologic toxicity OR >42 days for prolonged myelosuppression defined as ANC <500/ μ L or platelet count <10 x10⁹/L in a normal bone marrow with <5% blasts and no evidence of disease or dysplasia, will result in permanent discontinuation from treatment, unless the patient is demonstrating clinical benefit as agreed by the Investigator and Sponsor (Table 13).

Table 13. Recommended Dose Modification Criteria for Treatment-Related Toxicity [Monotherapy Cohort, Combination Cohort 1 and Expansion Cohort (Unfit Patients), Combination Cohort 2 (Fit Patients) and Continuation Cohort (Monotherapy Cohort)]

Drug	Toxicity	Grade 1	Grade 2	Grade 3	Grade 4
PF-04449913	Non Hematologic	Continue at the same dose level.	Continue at the same dose level. If persistent (at least 7 days) and not responding to optimal medical management, withhold dose until toxicity is grade ≤ 1 , then resume treatment at the same dose level or reduce the dose by 1 level at the discretion of the investigator.	Withhold dose until toxicity is grade ≤ 1 , or has returned to baseline, then resume treatment at the same dose level or reduce the dose by 1 level at the discretion of the investigator. (Nausea, vomiting or diarrhea must persist at Grade 3 or 4 despite maximal medical therapy to require dose modification).	Withhold dose until toxicity is grade ≤ 1 , or has returned to baseline, then reduce the dose by 1 level and resume treatment, or discontinue at the discretion of the investigator. (Nausea, vomiting or diarrhea must persist at Grade 3 or 4 despite maximal medical therapy to require dose modification).

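### Two of the four DLT criteria, including the only hematologic one, take longer to meet than the DLT observation window lasts, and neither document says how such events are counted

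*Protocol*

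**What the plan says.** Protocol Section 3.2 fixes the DLT observation period by day number:

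- Monotherapy Cohort: "the DLT observation period will be from Day -5 to Day 28 of Cycle 1".
- Combination Cohorts 1 and 3: "the DLT observation period will be from Day 1 to Day 28 of Cycle 1".
- Combination Cohort 2: "the DLT observation period will be from Day -3 to Day 21 or to Day 28 of the first induction cycle". Which end applies turns on the start of the following chemotherapy.

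The same section lists four DLT criteria. Criterion 2 is "Prolonged myelosuppression that lasts longer than 42 days from the point of detection", with a normal marrow. Criterion 4 is a delay of more than 28 "days in receiving the next scheduled cycle due to persisting non-hematologic toxicities".

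The decision rules are in Sections 3.1.1 and 3.1.2. For Combination Cohorts 1 and 3, if at most 1 of 6 patients "experiences a DLT by the end of Cycle 1, the tolerability of the combination will be deemed confirmed". The monotherapy 100 mg level and Cohort 2 use the same threshold, at the end of Cycle 1 and of Induction Cycle 1 respectively. Section 2.2 names first-cycle DLTs in the primary endpoint.

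The SAP adds nothing on timing. Section 6.2.1 refers back to Protocol 3.2. Section 8.2.1 tabulates DLTs in the lead-in period and first cycle. Protocol 9.1 and SAP 5.2 treat the first cycle and the DLT observation period as the same thing.

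Separately, Protocol 5.3.2 defines a cycle as 28 days unless toxicity prolongs it. Section 5.3.9 lets a cycle be "extended to a maximum of 56 days for non-hematologic toxicity, or to a maximum of 70 days if due to hematologic toxicity". Neither section is linked to the DLT window.

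**The concern.** A criterion that takes longer to meet than the period in which it may be met cannot contribute to the count. Criteria 2 and 4 appear to be in that position in every DLT cohort. The documents do not say that an event arising in the window and confirmed later counts, or that the count stays open.

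Criterion 2 carries most of the weight. Criteria 1, 3 and 4 are all restricted to non-hematologic toxicity, so criterion 2 is the only route by which myelosuppression can be a DLT, in cohorts where the drug is added to myelosuppressive chemotherapy. Elsewhere the protocol treats the same event, lasting more than 42 days, as a ground for stopping treatment (Table 13, Table 18).

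The DLT count is the formal basis for calling a regimen tolerable and is part of the primary endpoint. An omission here can only lower the count.

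**Working it through.** Protocol 9.2 gives no sample-size calculation for these cohorts, so there is no stated operating figure to reproduce. The check is calendar arithmetic. There is no Day 0.

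**Window lengths (Protocol 3.2).** Monotherapy: 5 + 28 = 33 days. Cohorts 1 and 3: 28 days. Cohort 2: 3 + 21 = 24 days, or 3 + 28 = 31 days. All are shorter than 42 days.

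**Criterion 2, most favourable case (detection on the first day of the window).**

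| Cohort | Detection | 42 days reached | First day beyond 42 | Window ends |
|---|---|---|---|---|
| Monotherapy | Day -5 | Day 38 | Day 39 | Day 28 |
| Cohort 2 | Day -3 | Day 40 | Day 41 | Day 21-28 |
| Cohorts 1 and 3 | Day 1 | Day 43 | Day 44 | Day 28 |

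Detection on Day 28 reaches 42 days on Day 28 + 42 = Day 70.

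**Criterion 4.** With a 28-day cycle the next one is due on Day 29. A 28-day delay runs to Day 29 + 28 = Day 57, so the criterion is met only after that. In Cohort 2, if a second induction is due on Day 22, the corresponding day is 22 + 28 = Day 50.

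**Does a prolonged Cycle 1 rescue the criteria?** Section 5.3.9 allows 70 days for hematologic toxicity (28 + 42) and 56 days for non-hematologic toxicity (28 + 28). A 70-day Cycle 1 could contain criterion 2 if detection came by about Day 27-28. Criterion 4 still fails, because a delay above 28 days makes the cycle longer than 28 + 28 = 56 days, beyond the longest cycle permitted for that reason.

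**What the size could be (illustration only).** Let a be the probability of a DLT inside the window and b the probability of a DLT met only under criterion 2 or 4. Then P(at most 1 of 6) = (1-p)^6 + 6p(1-p)^5, with p = a when late events are left out and p = a + b when they count. Neither a nor b is given in the documents; the values below are assumed.

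| a | Late events left out | b = 5% | b = 10% | b = 20% |
|---|---|---|---|---|
| 10% | 0.886 | 0.776 | 0.655 | 0.420 |
| 20% | 0.655 | 0.534 | 0.420 | 0.233 |

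Example, a = 20%, b = 10%: leaving late events out gives 0.8^6 + 6(0.2)(0.8^5) = 0.262 + 0.393 = 0.655. Counting them gives 0.7^6 + 6(0.3)(0.7^5) = 0.118 + 0.303 = 0.420. With b = 0 there is no difference.

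**The case against.** Four arguments can be made for the plan.

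1. *Attribution by onset is intended.* Criterion 2 runs from the point of detection, which fits detection in the window and confirmation later. This is plausible, but it is not written. If it is the intent, a count taken at the end of Cycle 1 is not final for a patient still cytopenic then, and the text still needs reconciling.

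2. *The decision rules refer to the end of Cycle 1, not Day 28, and a cycle can be prolonged.* This has force for criterion 2. It conflicts with the numbered Day 28 in Section 3.2 and does not help criterion 4. The 56- and 70-day limits are in Section 5.3.9, whose heading omits Cohort 3; that cohort's section, 5.3.10, states no such limits.

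3. *Late toxicity is still seen.* This stands. Adverse events are summarised for Cycle 1 and for later cycles (Protocol 9.5.1, SAP 8.2.4.1), and Protocol 9.6 provides ongoing review of adverse events and laboratory changes by sponsor and investigators. What is affected is the DLT count and the rule built on it.

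4. *Late-only DLTs are probably uncommon.* Criterion 2 requires a normal marrow. A toxicity that delays the next cycle by more than 28 days will often already satisfy criterion 1 or 3. Protocol 1.2.8.1 reports 2 of 41 evaluable patients with DLTs in B1371001, both non-hematologic, and none among 23 patients given the LDAC combination in B1371003. The DLT definitions of those studies are not shown, so this is indicative only, but it gives no support to the larger values of b.

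**Conclusion.** The inconsistency is real and affects every DLT cohort. On the numbered window, criteria 2 and 4 fall after the window closes even in the most favourable case. Any resulting bias is one-directional, towards confirming tolerability. Its size cannot be derived from the documents; the illustration rests wholly on assumed rates, and the effect vanishes if no patient has a late-only DLT.

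A reader might infer more: that prolonged myelosuppression can never count on any reading, that late toxicity escapes the trial, or that tolerability was wrongly declared. The documents do not support these. The prolonged-cycle wording could admit criterion 2, late toxicity is captured in the safety summaries and ongoing review, and nothing shows that any patient met criterion 2 or 4 after Day 28. The supportable point is that the window, criteria, decision text and SAP table do not fit together, and that the primary-endpoint DLT count depends on a rule nobody has written down.

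**What to change.** Reconcile four places: the window and criteria in Protocol 3.2; the decision text in 3.1.1 and 3.1.2; the cycle-prolongation text in 5.3.2 and 5.3.9; and SAP 8.2.1. The reconciled text should state two things:

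- **One attribution basis for criteria 2 and 4.** For example, toxicity arising in the first cycle is attributed to it, including a delay of the next cycle caused by that toxicity, with confirmation allowed after Day 28. The delay needs explicit mention because it normally begins on Day 29, so wording limited to events that start inside the window would miss it.
- **When the DLT count is final.**

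Tabulate the primary-endpoint DLTs in SAP 8.2.1 on that basis. Check the existing data for any first-cycle toxicity that met criterion 2 or 4 after Day 28, and report the number found, including zero.

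The DLT criteria and clinical thresholds do not change. The cost is a few sentences and one data check; the downside is that a count may become final later. Protocol 1.2.8 reports 45 patients already treated, of at most 49, so the main remaining effect is on the DLT tabulation.
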